### **Planned Interim Analysis**

No interim analyses are planned.

### **Subgroup Description**

Outcomes will be assessed for subgroup characteristics by treatment group if they are found to be statistically significant. The baseline factors will include:

- Baseline HbA1c
- Baseline glucose
- Age
- Sex
- Race/ethnicity
- Insurance status
- Diabetes type
- Kidney disease
- Corticosteroid use
- Pre-study insulin use

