	
Glycemic events above 300 mg/dl and below 54 mg/dl
 
Glycemic variability (coefficient of variation)
 
Differences in treatment effect according to individual characteristics (age, sex, BMI, HbA1c, renal function, and type of diabetes).
 
Proportion of participants that spend >70% of time in target range (70-180 mg/dl) without hypoglycemia
 
Significant hyperglycemic events (glucose >400mg/dl)

	
Key Safety Outcomes:
 
 
• Reportable hypoglycemia: glucose level <40mg/dl (POC or central lab) defined as an event that required assistance due to altered consciousness to actively administer parenteral dextrose or glucagon. This means that the participant was impaired cognitively to the point that the participant was unable to drink or eat oral carbs (e.g. juice, crackers), was incoherent, disoriented, and/or combative, or experienced seizure or coma.
 
• Diabetes-related ketoacidosis (DKA) or hyperosmolar hyperglycemic syndrome (HHS)
 

Participant Duration	Up to 10 days during the inpatient stay; optional extension of wear at investigator discretion (up to 10 additional days)
Funding Source	NIDDK

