#### Sample Size

The assumptions for the sample size calculations were as follows: (1) normality of the response variable, i.e., % TIR; (2) two-sided test of superiority; (3) a difference in response of 15%; (4) standard deviation of 16%; (5) 99% power; (6) two-sided type I error rate of 5%; and (7) 1:1 allocation ratio between AID and multiple daily injections (MDI).

A sample size of N=100 gives a power of 99% to detect a difference of 15% at a standard deviation of 16% and  $\alpha=0.05$  based on our pilot trial. To account for patients not completing 24hrs on device and to allow for a minimum sample of 20 participants with T1D we will enroll up to 135 participants. We anticipate a larger effect, a roughly 20% difference in time in range (TIR) among participants with T1D and we will have 80% power to detect a 20% or larger difference in TIR with 10 participants with T1D per group, which is sufficient for an exploratory analysis.

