### **Multiple Comparison/Multiplicity**

Type I error rate inflation will be controlled in the primary and secondary outcomes using a hierarchical system.

For the exploratory subgroup analysis of diabetes subtypes, the Benjamini-Hochberg method of FDR adjustment will be used to account for potential multiplicity.

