### **Exploratory Analyses**

As a subgroup analysis, differences in treatment effect will be examined. Including comparisons of treatment across BMI ranges, sex, HbA1c, steroid use, and renal function. It is expected most cases (~80%) will be T2D cases. To explore differences in treatment effect among participants with T1D we will enroll a minimum of 20 participants with T1D.

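### Subgroup assessment hangs on an undefined significance condition that contradicts the rest of the SAP and permits selective subgroup results

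*SAP*

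**What the plan says.** Three places in the SAP describe the subgroup work.

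- **Subgroup Description** sets a condition: "Outcomes will be assessed for subgroup characteristics by treatment group if they are found to be statistically significant". It then lists ten factors: baseline HbA1c, baseline glucose, age, sex, race/ethnicity, insurance status, diabetes type, kidney disease, corticosteroid use and pre-study insulin use.
- **Exploratory Analyses** sets no condition: "As a subgroup analysis, differences in treatment effect will be examined". It continues: "Including comparisons of treatment across BMI ranges, sex, HbA1c, steroid use, and renal function", and sets a minimum of 20 participants with T1D.
- **Table 1** makes treatment-effect differences part of the secondary objectives and lists them among the other secondary and exploratory endpoints, again with no condition: "Differences in treatment effect according to individual characteristics (age, sex, BMI, HbA1c, renal function, and type of diabetes").

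On multiplicity, the SAP says: "Type I error rate inflation will be controlled in the primary and secondary outcomes using a hierarchical system". Subgroup tests are not on that hierarchical list. For subgroups it adds: "For the exploratory subgroup analysis of diabetes subtypes, the Benjamini-Hochberg method of FDR adjustment will be used to account for potential multiplicity". No adjustment is named for any other factor.

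**The concern.** The condition in Subgroup Description names no test, model or level, and its pronoun can refer to either of two things. Two analysts could follow the sentence faithfully and produce different outputs, with the choice made after seeing the data.

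- If the subgroup factors must be significant, results are selected on their own p-values. In subgroups this small, the estimates that survive such a filter are inflated.
- If the outcomes must be significant, a non-significant TIR result cancels the T1D analysis. The plan sets a recruitment minimum for that analysis and quotes a power figure for it.

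Either reading conflicts with the unconditional statements in Table 1 and Exploratory Analyses. Separately, false-positive control is attached to one factor although ten or eleven are to be examined. At stake is how far a reader can trust the subgroup findings. The primary comparison is not at stake.

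**Working it through.** **Inputs.** SD of TIR 16, two-sided alpha 5% and 1:1 allocation (Sample Size). T1D effect 20 points with 10 per group, and design difference 15 points overall (Sample Size). Total 120 (Section II). About 80% T2D expected (Exploratory Analyses). The split of T1D from T2D within the 120 is my assumption, shown at two values.

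**The plan's own subgroup figure.** Power for 20 points with 10 per group at SD 16: SE = 16 × √(1/10 + 1/10) = 7.16, and Φ(20/7.16 − 1.96) = 0.798. This matches the stated 80% and the 0.798 in Table 4. It is power for a treatment effect within T1D, not for a difference in effect between T1D and T2D.

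**Interaction implied by the plan.** If 15 is the average effect over all 120 and 20 is the T1D effect:

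- 20 T1D, 100 T2D: T2D effect = (15 × 120 − 20 × 20)/100 = 14, so the interaction is 6 points.
- 24 T1D, 96 T2D (80% T2D): T2D effect = (15 × 120 − 20 × 24)/96 = 13.75, so the interaction is 6.25 points.

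**Smallest observed interaction that reaches p < 0.05.**

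| Split | SE | 1.96 × SE | Implied interaction | Ratio |
|---|---|---|---|---|
| 20 / 100 | 16 × √(2/10 + 2/50) = 7.84 | 15.4 | 6 | 2.6 |
| 24 / 96 | 16 × √(2/12 + 2/48) = 7.30 | 14.3 | 6.25 | 2.3 |

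The ratio is that of the smallest significant estimate in the expected direction to the implied interaction. For the 20/100 split, power is 25% for a true interaction of 10 points and 72% for 20 points; 80% power needs about 22 points. A significance filter would therefore drop most moderate interactions that are real.

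**Factor lists.** I count kidney disease and renal function as one factor.

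- Table 1: six factors, including BMI.
- Subgroup Description: ten factors, without BMI.
- Exploratory Analyses: BMI, sex, HbA1c, steroid use and renal function, plus T1D.
- Merged: eleven distinct factors.

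**Unadjusted tests.** Taking diabetes type out leaves 9 of 10 factors, or 10 of 11 with BMI. With one test per factor at 5%, one outcome and independence:

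- 9 factors: 1 − 0.95⁹ = 0.370
- 10 factors: 1 − 0.95¹⁰ = 0.401

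Positive correlation, plausible among HbA1c, baseline glucose and pre-study insulin use, lowers these figures. Testing more than one outcome raises them.

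**Corticosteroid use.** Subgroup Description introduces its list with "The baseline factors will include", and corticosteroid use is on it. Baseline Descriptive Statistics instead records that variable as use during the trial, which may arise after randomization.

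**The case against.** The strongest reply is that the grammatical subject of the sentence is the outcomes. On that reading it is a gate: subgroups are explored only for outcomes that showed an overall effect, which restrains fishing. With 99% power claimed for TIR, the gate would seldom block the T1D analysis under the plan's own assumptions. The work is also labelled exploratory throughout, and the confirmatory hierarchy is untouched. Much of this stands. It does not remove the ambiguity or the conflict with the two unconditional passages, and an exploratory label does not justify selection by p-value.

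Four stronger inferences are tempting, and the SAP does not support them.

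- A reader might infer that subgroup results will be selectively reported. That depends on one of two readings. The sentence says nothing about reporting, and other sections plan the examination unconditionally. The wording permits selection but does not require it.
- A reader might infer that Benjamini-Hochberg on diabetes subtype is an adjustment over a single test and so does nothing. The SAP does not define the family, which could span several outcomes or subtype comparisons. The fault is that it is undefined.
- A reader might subtract 15 from 20, take the interaction as 5 points, and conclude that the overstatement is at least threefold (15.4/5). But 15 is the overall difference, not the T2D effect, and the implied interaction is about 6.
- A reader might infer that adjustment across all exploratory interactions is obligatory. Declaring the p-values unadjusted and descriptive is equally acceptable.

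**Conclusion.** The point holds as a badly fixed rule and an internal contradiction. The significance condition has no defined referent, test or level, and conflicts with Table 1 and Exploratory Analyses; the three factor lists also disagree.

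Under the factor reading, a T1D interaction would have to be observed at about 14.3 to 15.4 points to pass, against about 6 implied: an overstatement of roughly 2.3- to 2.6-fold. This rests on SD 16, a total of 120, equal arms within subgroups, a normal approximation, and treating the 15-point design difference as the overall effect. The plan uses 15 for powering and does not clearly offer it as a forecast. Under the outcome reading, the cost is loss of the planned T1D analysis whenever TIR is not significant.

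The 37–40% chance of a false positive is per outcome and assumes independent tests, so with positive correlation it is an upper figure. Because the analyses are exploratory, the missing adjustment is the lesser part of the point. The primary conclusion does not depend on any of this.

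**What to change.** 1. Delete the significance condition from Subgroup Description.
2. Replace the three lists with one fixed list of baseline factors merging Table 1, Subgroup Description and Exploratory Analyses. Define corticosteroid use as status at randomization, or flag it as a post-randomization variable.
3. For each factor, add a treatment-by-factor interaction to the primary TIR model. Report every interaction and every subgroup estimate with its 95% CI, whatever the p-value.
4. Either apply Benjamini-Hochberg across all the interaction tests, or state that all subgroup p-values are unadjusted and exploratory.

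The cost is SAP wording and one forest plot. If adjustment is chosen, the exploratory p-values become somewhat larger. Design, enrolment and the primary analysis do not change.

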### **Multiple Comparison/Multiplicity**

Type I error rate inflation will be controlled in the primary and secondary outcomes using a hierarchical system.

For the exploratory subgroup analysis of diabetes subtypes, the Benjamini-Hochberg method of FDR adjustment will be used to account for potential multiplicity.

### **Exploratory Analyses**

As a subgroup analysis, differences in treatment effect will be examined. Including comparisons of treatment across BMI ranges, sex, HbA1c, steroid use, and renal function. It is expected most cases (~80%) will be T2D cases. To explore differences in treatment effect among participants with T1D we will enroll a minimum of 20 participants with T1D.

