**Table 3. Minimum detectable differences**

Total N	Min. Detectable Difference
14	32.7%
20	26.5%
30	21.2%
44	17.3%
60	14.7%
128	9.99%

T1D, due to its low incidence compared to T2D, will be a difficult subgroup to analyze with any statistical rigor (e.g., if 14 participants with T1D are enrolled, a mean difference of 32.7% would have to be observed to achieve 90% power). We anticipate a roughly 20% difference in time in range (TIR), among participants with T1D. We will have about 80% power to detect a 20% or larger difference in TIR with 10 participants with T1D per group, which is sufficient for an exploratory analysis. We aim to include at least 20 participants in subgroups of interest (T1D, steroid exposure, kidney disease).

Looking at N=56, 72, and 100, standard deviation=16% - 17.3%, and mean differences in % TIR ranging from 10-20%, we calculated the power and found in all scenarios we would achieve greater than 90% power to find a difference larger than 15% for the primary endpoint, **Table 4**.

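### The subgroup plan asks whether the treatment effect varies between patients, but it names no interaction analysis and supports 20 per subgroup with a within-T1D test against zero

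*SAP*

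**What the plan says.** The SAP's Table 1 makes effect modification a secondary objective and lists among its endpoints "Differences in treatment effect according to individual characteristics", naming age, sex, BMI, HbA1c, renal function and diabetes type. The Exploratory Analyses section opens with the same aim, compares treatment across BMI ranges and other factors, and closes with "To explore differences in treatment effect among participants with T1D we will enroll a minimum of 20 participants with T1D".

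The Subgroup Description section says "Outcomes will be assessed for subgroup characteristics by treatment group", and the rest of that sentence makes this conditional on statistical significance. It does not say what must be significant or by which test. No section names a treatment-by-factor interaction.

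The subgroup size is justified in two places. Under Table 3 the SAP says "We will have about 80% power to detect a 20% or larger difference in TIR with 10 participants with T1D per group" and extends the target to other groups: "We aim to include at least 20 participants in subgroups of interest (T1D, steroid exposure, kidney disease". The Sample Size section repeats the claim: "with 10 participants with T1D per group, which is sufficient for an exploratory analysis".

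The Multiple Comparison/Multiplicity section applies a Benjamini-Hochberg adjustment to the exploratory analysis of diabetes subtypes.

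**The concern.** Two different contrasts are in play. Whether AID works in people with T1D is a within-subgroup comparison against zero. Whether AID works differently in T1D than in other patients is a difference between two treatment differences, and its variance is larger. The SAP asks mainly the second question and gives power only for the first.

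This matters for how the results will be read. The text names no interaction and has an undefined significance condition, so an analyst could fit each subgroup separately and take one significant and one non-significant result as evidence that the effects differ. With subgroups of very unequal size, that pattern arises often when the effects are the same. A condition that decides by significance which subgroups are assessed also selects results for reporting. Cutting BMI into ranges discards information and leaves the cut-points open.

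**Working it through.** **Inputs, all from the SAP.** Two-sided 5% error and 1:1 allocation (Sample Size); SD 16 from the pilot or 17.3 from prior studies (section II); 20 points anticipated in T1D (text under Table 3); 15 points overall (Sample Size); at least 20 T1D participants among 120 with sufficient data (section II). I take the SD as equal in all strata, without covariate adjustment, and arms balanced within each stratum.

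**1. Reproduce the stated 80%.** With 10 per arm, SE = SD × √(2/10).
- SD 16: SE = 7.16; 20/7.16 = 2.80; power = Φ(2.80 − 1.96) = 0.798.
- SD 17.3: SE = 7.74; 20/7.74 = 2.59; power = 0.734.

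Both match the N=20 column of Table 4, so the 80% is AID against control inside T1D, by normal approximation, at SD 16. A t-test with 18 df gives 0.753 and 0.686.

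**2. Precision of the difference in effects.** With 20 T1D and 100 others, SE = SD × √(4/20 + 4/100) = SD × 0.490.

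| | SD 16 | SD 17.3 |
|---|---|---|
| SE (points) | 7.84 | 8.48 |
| 95% CI half-width, 1.96 × SE | 15.4 | 16.6 |
| Gap with 80% power, 2.80 × SE | 22.0 | 23.7 |

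These figures need no assumption about the true gap. If T1D made up 20% of 120 (24 and 96), the SEs would be 7.30 and 7.90 and the half-widths 14.3 and 15.5.

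**3. Power of the interaction by true gap (20 and 100).** The SAP states no T2D effect, so the gap is an assumption. It is 5 points if 15 is taken for the others. It is 6 points if 15 is the overall average, because (20 × 20 + 100 × 14)/120 = 15.

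| Assumed gap | SD 16 | SD 17.3 |
|---|---|---|
| 5 | 0.098 | 0.091 |
| 6 | 0.119 | 0.109 |
| 10 | 0.248 | 0.219 |
| 15 | 0.482 | 0.425 |
| 20 | 0.723 | 0.655 |

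**4. Comparing separate results when the effects are equal.** Let the true effect be 15 points in both types. Table 4 gives power 0.554 (SD 16) or 0.492 (SD 17.3) for N=20, and 0.997 or 0.990 for N=100. The chance of a significant result in T2D with a non-significant one in T1D is:
- SD 16: (1 − 0.554) × 0.997 = 0.44
- SD 17.3: (1 − 0.492) × 0.990 = 0.50

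With t-tests the two figures are 0.49 and 0.54.

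**5. The other two subgroups.** The target of 20 is also set for kidney disease and steroid exposure, for which the SAP anticipates no 20-point effect. At the 15-point planning effect, Table 4 gives 0.49 to 0.55 for a group of 20.

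**The case against.** The SAP labels this work exploratory, concedes that T1D is hard to analyse rigorously, and already words the 80% as a within-T1D figure. Table 4 already prints the 0.492 and 0.554. The last sentence of Exploratory Analyses can be read as the AID-control difference within T1D, and for that the 80% is the right quantity. The opening aim is compatible with an interaction model, and nowhere does the SAP say it will compare subgroup p-values. All of this stands, and it means that restating the power alone would change little. It does not supply the missing interaction or define the significance condition. The first sentence of Exploratory Analyses and both entries in Table 1 favour the effect-modification reading.

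A reader might infer three stronger things that the SAP does not support.
- *The design has about 10% power for its subgroup question and the results will mislead.* The 10% depends on a gap of 5 to 6 points that the SAP never states; power is 22% to 25% at 10 points and 66% to 72% at 20. Misreading also requires someone to compare separate p-values.
- *Table 5 refutes a larger effect in T1D.* Its T1D rows differ by 11 points (65 − 54) and its inpatient T2D closed-loop rows by 24.3 (65.8 − 41.5). The T1D rows have a sensor-augmented comparator and a population over 6 years old, and are not marked inpatient. They neither support nor refute the anticipated 20.
- *At least one of the three target subgroups will very probably miss significance.* The Table 4 powers give 1 − 0.554³ = 0.83 and 1 − 0.492³ = 0.88, but only for three non-overlapping subgroups of exactly 20. The target is a floor, and one patient can belong to all three.

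**Conclusion.** The point holds as a minor one. The SAP asks whether the effect varies, names no analysis that answers this, and cites a power figure for another contrast. With 20 T1D participants and 100 others, the difference in effects can be estimated only to within about ±15 to ±17 points, and 80% power needs 22 to 24 points. Reading separate subgroup tests side by side would suggest a difference between T1D and T2D about half the time when both have the same 15-point effect.

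The figures rest on an SD of 16 to 17.3 common to all strata, balanced arms within strata and no covariate adjustment. The SAP reports subgroup SDs of up to 25 in a prior trial; at 25 the SE is 12.25 and the half-width about 24 points. The primary analysis and the hierarchical tests are not affected.

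**What to change.** **Subgroup Description and Exploratory Analyses**
- Remove the significance condition.
- Judge effect modification by the treatment-by-factor interaction, fitted on all participants in the model given under Analysis of Percent Time in Range, and report the estimate and 95% CI for every listed factor. The factor lists in Table 1 and these two sections differ (BMI is absent from Subgroup Description), so settle on one list.
- Show within-subgroup estimates with CIs as description only.
- Enter BMI, HbA1c, age and eGFR as continuous modifiers and use ranges for display.

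**Multiple Comparison/Multiplicity**
- Keep the Benjamini-Hochberg adjustment and apply it to the interaction p-values.

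**Section II (text under Table 3) and Sample Size**
- Beside the 80%, add the 95% CI of about ±15 to ±17 points for the difference in effects with 20 T1D and 100 others, and the 22 to 24 points needed for 80% power.
- As illustration, give power of 9% to 12% for an assumed gap of 5 to 6 points and 22% to 25% for 10 points.
- Point to the 0.49 to 0.55 in Table 4 for any 20-person subgroup at 15 points.

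The cost is SAP wording and minor programming. The downsides are a less favourable stated figure and a linearity assumption for the continuous modifiers, which the display by ranges can check. No extra patients are needed.
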